19.	19. Dissemination of research findings 39		
20.). References		

2. Glossary

Linear growth faltering / short stature / stunting

Children are defined as having short stature, otherwise known as linear growth faltering or stunting, if their height-for-age is more than two standard deviations below the population median height.

Linear growth faltering also encompasses reduced growth velocity, which is defined as a growth velocity of less than the 10th percentile, or the growth curve crossing 2 SD lines or centiles on a growth chart.

ASQ-3

Ages and Stages Questionnaire, third edition. Standard instrument used in the Healthy Child Programme to assess early child development in children aged one month to 5 and a half years.

GMDS

Griffiths Mental Development Scale. Development measure administered by child psychologists.

NCMP

National Child Measurement Programme.

3. Signature page

CI Agreement			
The study, as detailed within this Research Protocol, will be conducted in accordance with the principles of GCP, the UK Policy Framework for Health and Social Care Research, and the Declaration of Helsinki and any other applicable regulations. I delegate responsibility for the statistical analysis and oversight to a qualified statistician (see declaration below).			
CI name:	[name]		
	1		
Signature:			
Date:	9 Th September 2022		
Statistician's Agreement			
The study as detailed within this research protocol will be conducted in accordance with the current UK Policy Framework for Health and Social Care Research, the World Medical Association Declaration of Helsinki (1996), Principles of ICH E6-GCP, ICH E9 - Statistical principles for Clinical Trials and ICH E10 - Choice of Control Groups.			
	statistical work in this protocol is accurate and take alysis and oversight in this study.		
Statistician's name:	[name]		
Signature:			
Date:	9 th September 2022		

4. Summary and synopsis

Short title	Child growth in east London			
Methodology	Pilot growth screening programme of 630 children recruited from Tower Hamlets, East London			
	The overarching objective of this grant is to detect linear growth failure early in childhood by employing an automated growth screening algorithm for pre-school age children. The screening algorithm will be created using national data and piloted for feasibility and acceptability in Tower Hamlets, East London. We have two interlinked aims, with the following			

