6.4. Secondary endpoints

• Linear growth trajectory

This will be assessed by child height measurements at age 2-2.5 years, age 2.5-3.5 years, and age 4-5 years, in combination with target parental height. Parents who make use of the app will provide additional longitudinal growth measurements between age 2-5 years. All measurements will be entered into an algorithm, developed using data from two longitudinal UK cohorts (Millennium Cohort Study and Born in Bradford), which will identify children with poor linear growth based on absolute height, growth velocity and distance from target height.

• Child development at age 2-2.5 years.

This will be assessed using the ASQ-3 questionnaire and the GMDS, as described above.

7. Study population

This study will enrol a cohort of 630 children living in Tower Hamlets into a pilot screening programme at age 2.0-2.5 years and apply a growth-screening algorithm to identify children with poor growth. Children will be selected randomly from health visitor records in Tower Hamlets to ensure a representative sample, based on the inclusion and exclusion criteria outlined in section 7.1 and 7.2. We will include all children whose caregivers are willing to provide written informed consent to i) have a height/weight measurement (+/- a developmental assessment) together with a baseline questionnaire undertaken at age 2.0-2.5 years (by the health visitor) and a repeat weight/height measurement at age 2.5-3.5 years (either by the health visitor as an additional visit or by the GP surgery at the time of pre-school vaccinations); ii) undergo longitudinal growth screening by the parent using an app which measures a child's height; and iii) have the child's identifiers sent to Tower Hamlets Local Authority in order to access their weight/height measurement undertaken at school at age 4.0-5.0 years through the NCMP programme, to prove feasibility of data linkage. We will work in partnership with Tower Hamlets GP Care Group to identify a representative sample of children from the borough based on health visitor lists, to ensure we minimise bias and include even the hardest-to-reach participants.

We will also conduct a secondary analysis of a clinical sample of ~200 children with confirmed growth disorders e.g. Growth Hormone Deficiency, growth failure associated with small for gestational age and Turner syndrome (clinical sub-study).

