Children will have a further height measurement at approximately 3.0 years by the health visitor. If the preschool health visiting contact is not operational at the time, the child will instead have their height measured by the nurse/healthcare assistant administering the immunisations at the preschool booster appointment at their GP practice, or at a planned research visit appointment Through the health visitor contact at 3.0 years children will have a repeat developmental assessment using the ASQ-3 questionnaire. Data will be collected using **CRF 2 (Follow-up visit).** Child height will be assessed using the same tool as at baseline. If there are any missing parental heights a further attempt will be made to measure or record an estimated height. Families will be occasionally contacted by the study team by phone to improve retention in the study and to remind caregivers about the smartphone app.

School entry measurement (age 4-5 years)

Child height and weight will be recorded as part of the routine NCMP programme at school entry (4-5 years of age). We will provide identifiers to Tower Hamlets Local Authority to enable them to link the NCMP measurement to enrolled children and provide us with their heights and weights recorded at 4-5 years of age. This is a

feasibility piece to see if data could be used from NCMP in a larger screening programme. We will also collect data on school enrolment, and screen for educational concerns by health visitors screening school nursing notes to review if there has been any input from a special educational needs co-ordinator at school. After the NCMP measurement, we will distribute questionnaires for caregivers and health visitors to collect data on feasibility and acceptability of the study procedures. We will also conduct focus groups with small groups of participants (see below).

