At each of the 3 measurements of height we will identify the 2-3% of children with the poorest growth, as categorised by the algorithm (based on parental height, child height, and child growth velocity), in whom prior studies show a high prevalence (30-40%) of medical disorders. We will contact parents of these children to offer referral to the paediatric endocrinology clinic at the Royal London Hospital. A member of the study team will call the parents to inform them and will write to the child's GP to request a referral into the Royal London Hospital clinic via the e-referral system. We will evaluate acceptability and feasibility of the screening and referral process, using parental and primary care staff questionnaires. We will evaluate uptake by calculating the proportions screened, referred, investigated in clinic and diagnosed with medical disorders. At the clinic, children will be assessed by a paediatric endocrinologist and will undergo routine medical evaluation for short stature, with appropriate follow-up.

Development sub-study (age 2.0-2.5 years):

A random sample of 150 children will also be invited to enrol in a sub-study to generate pilot data on the sensitivity of the parent-reported ASQ-3 to assess child development compared to a gold standard development battery, the GMDS, undertaken by a psychologist. These children will undergo a neurodevelopmental assessment during their routine health visitor visit of their motor, cognitive, language and social skills using a standardized test battery (GMDS) by a child psychologist. Using data from the ASQ-3 developmental assessments conducted at baseline and follow up visits by the health visitor, we will investigate relationships between growth and development and assess content validity of the ASQ-3 by comparing it with the GMDS.

[figure not shown]
Qualitative sub-study (following the 2-2.5 year visit)

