9.5 Follow-up procedures

Participants who have short stature for their age and parental heights will be identified using the screening algorithm at baseline. These participants will be referred for further clinical investigation. At follow-up, growth velocity will also be included in the screening algorithm, and any children found to have reduced growth velocity will be referred. Children will be followed up in a dedicated research clinic within Barts Health NHS Trust. [name] clinic is an established paediatric endocrine/growth clinic at the Royal London Hospital. Children will be seen and assessed as per standard clinical practice. They will have auxological assessment (height, weight, head circumference and recording of parental heights), a clinical review (history and physical examination). Patients requiring further investigations for short stature will follow a current best practice guideline investigation protocol. More detailed genetics (if a specific genetic disorder is suspected), Growth Hormone testing (as per standard departmental protocols) or referral to another speciality (e.g. gastroenterology) may be requested if clinically indicated.

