We will employ an algorithm based on previous methodology, using variables individually and in combination, after checking for co-linearity. Different cut-off values will be chosen and the proportion of the population judged to have linear growth failure estimated for each cut-off. We will then examine the detection rate for each cut-off by applying it to data from ~200 local children treated in the specialist paediatric endocrinology centre with known growth disorders e.g. Growth Hormone Deficiency (GHD), Turner Syndrome (TS) and Small for Gestational Age without catch-up growth (SGA). Consent will be obtained retrospectively from these patients and their parents/carers to link their routinely obtained clinical data (diagnosis, age at diagnosis, height and parental height) to previously height data obtained at school entry via the NCMP. To do this linkage, the hospital clinical data (and the associated NHS number or other identifiers) will be shared with NHS England. This will allow us to calculate sensitivity-and-specificity algorithm cut-offs for the detection of these conditions. This will enable a trade-off between detection rate (sensitivity) and the false positive rate (1-specificity) to be evaluated. Additionally, the time elapsed from the first abnormal screening result until the clinical diagnosis of growth hormone deficiency will be related to the cut-off values.

The outcomes for Aim 1 are age of identification of stunting (which will be reported but the study is not powered to detect age of diagnosis); feasibility of measuring children in the community; the percentage of children referred; the percentage of children found to have underlying medical conditions; and the feasibility, acceptability and inter-test variability of a smartphone app and stadiometer height measures.

The algorithm will be applied to measures collected from each child at each visit, with children who are identified by the algorithm as being in the bottom 2% for height or

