growth being referred to clinic for further investigation. The proportion of children with complete observations, including height at three time points and parental height, will be compared to the proportion of children with fewer observation points or missing parental height. Descriptive statistics will be reported: the number and percentage of children found to be stunted and their characteristics (height, gender, age, socio-demographic factors). We will also report the number of children referred to clinic, attending clinic and found to have underlying medical conditions. The age at which each condition is identified will be reported and compared to the average age at diagnosis.

Height data collected by parents using a smartphone app will be analysed. The number of parents consenting to use of the smartphone app and reporting one or more height measurements through the app will be reported. The number of time points at which parent's upload smartphone measured heights will also be reported. Inter-rater reliability between parent-measured height using the smartphone app and Health Visitor measured height using a stadiometer will be assessed using Gwet's Agreement Coefficient.¹⁹

Aim 2

All children will undergo a developmental assessment in the community, conducted by a health visitor with input from the child's parent, as part of standard care (ASQ-3 questionnaire). A subset of 150 children will, in addition, have a gold standard developmental assessment conducted by a child psychologist using the GMDS, which measures gross motor, fine motor, social, language, visual-spatial and practical reasoning skills.

Data on socioeconomic circumstances will be used to model the probability of a child's risk of developmental delay or sub-threshold delay on the ASQ-3 (n=600) and GMDS (n=150). Poor growth (assessed by the algorithm) will then be included in these models to assess whether model fit is improved, and whether poor growth contributes to the predictive power of socioeconomic variables to predict developmental delay.

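### Aim 2 adds growth to the delay models only as an algorithm category; a continuous-growth model beside it would pick up a graded association at little cost

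*Protocol*

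**What the plan says.** Section 10.2, Aim 2, first models delay on the ASQ-3 (n=600) and the GMDS (n=150) from socioeconomic data. Growth then enters: "Poor growth (assessed by the algorithm) will then be included in these models to assess whether model fit is improved". The same sentence asks whether poor growth adds predictive power. No other growth term is named for these models.

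The hypothesis in section 6.2 and the Aim 2 outcomes at the end of section 10.2 are wider. They speak of growth data and anthropometric data in general.

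On what the algorithm category is, the protocol gives several pointers:
- For referral, section 9 (school entry measurement) takes "the 2-3% of children with the poorest growth, as categorised by the algorithm", and section 10.2, Aim 1, takes children "identified by the algorithm as being in the bottom 2% for height or" growth. Section 10.1 expects 12 of 600.
- Section 10.2, Aim 1, also says several cut-offs will be tried.
- The Introduction (section 5) sets severely affected children, who are referred, apart from a larger group whose poor growth has no medical cause.
- The Glossary counts height more than 2 SD below the median, and also "a growth velocity of less than the 10th percentile".
- Section 6.4 says the algorithm works "based on absolute height, growth velocity and distance from target height". Section 9.5 uses height and parental heights at baseline, and adds: "At follow-up, growth velocity will also be included in the screening algorithm".

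Development is measured again later. At the 3.0-year health visitor contact "children will have a repeat developmental assessment using the ASQ-3 questionnaire", and the development sub-study text plans to relate growth to development "Using data from the ASQ-3 developmental assessments conducted at baseline and follow up visits by the health visitor".

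**The concern.** The algorithm is built from continuous quantities, and its referral cut-off was chosen to find medical disorders. Aim 2 asks a different question: whether growth helps to identify children with delayed development. If risk rises gradually as growth worsens, a yes/no flag treats all unflagged children as alike and rests the comparison on a few flagged ones. The model may then show no clear improvement in fit although growth is informative. The pilot is meant to inform a larger application, so a near-null result that came from the coding of growth could be carried forward as evidence that growth adds nothing.

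**Working it through.** **1. The plan's own figure.** 0.02 × 600 = 12, as in section 10.1. At 3% it is 18. In the GMDS model (n=150) the flag would cover 3 to 4.5 children.

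**2. How wide the flag could be.** The 2 SD height rule alone flags 2.3% (14 of 600) if local heights match the reference. If the local mean is 0.25 or 0.5 SD lower (assumed shifts), it flags 4.0% (24) or 6.7% (40). Distance from parental height at baseline, and velocity at follow-up, could widen it further. Cut-offs from 2% to 10% are therefore examined.

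**3. Information kept.** For a normally distributed score cut at its lowest fraction q, the share of linear information kept is φ(z_q)² / [q(1−q)].
- q = 0.02: 0.0484² / 0.0196 = 0.120
- q = 0.03: 0.0680² / 0.0291 = 0.159
- q = 0.07: 0.1343² / 0.0651 = 0.277
- q = 0.10: 0.1755² / 0.0900 = 0.342

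**4. Power at n=600.** The protocol gives no delay prevalence, effect size or test level for Aim 2. Assumed: prevalence 10-30%, log-odds linear in the growth score, one socioeconomic covariate (log odds ratio 0.4), likelihood-ratio test at 5%. Simulated with 2,000 replicates per cell; ranges run over prevalence.

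| OR per SD | 2-3% flag | 7% flag | 10% flag | One continuous score |
|---|---|---|---|---|
| 1.3 | 12-21% | 19-34% | 23-39% | 48-82% |
| 1.5 | 24-47% | 41-68% | 46-76% | 82-99% |
| 2.0 | 57-87% | 82-98% | 89-99% | over 99% |

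Check by formula: the noncentrality is λ = n p(1−p)(ln OR)², multiplied by the share in step 3 for a flag. At OR 1.5, (ln 1.5)² = 0.1644.
- p = 0.10: λ = 600 × 0.09 × 0.1644 = 8.88, power 85%. For a 2% flag, λ = 8.88 × 0.120 = 1.07, power 18%.
- p = 0.30: λ = 600 × 0.21 × 0.1644 = 20.7, power over 99%. For a 3% flag, λ = 20.7 × 0.159 = 3.29, power 44%.

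This agrees with the simulation to within a few points. With about 12 flagged children the 5% test is itself only roughly calibrated: simulated size for the 2% flag was 1.8-8.9%.

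**5. Without a test.** At OR 1.5 per SD, the expected odds ratio of a 2% flag is 1.5^(0.0484/0.0196) = 2.72. With 10% prevalence, risk is about 0.227 in the 12 flagged children and 0.097 in the other 588. SE² = 1/(12 × 0.1755) + 1/(588 × 0.0879) = 0.494, so the 95% interval is about 0.7 to 10.8. The continuous odds ratio has SE = 1/√(600 × 0.09) = 0.136 and an interval of 1.15 to 1.96.

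**6. Where the flag wins.** If risk jumps only in the flagged 2%, a step odds ratio of 5 is found with 61-76% power by the flag and 16-18% by the continuous score. For a step odds ratio of 3 the figures are 30-47% and 9-11%.

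**7. The price of more than one continuous term.** If height SDS carries the whole effect, adding distance from target height leaves λ unchanged but uses 2 df. By the same formula, power at n=600 is 39-75% (OR 1.3) and 76-99% (OR 1.5). With velocity at follow-up (3 df) it is 34-69% and 70-98%.

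**8. GMDS, n=150.** In simulation one continuous score gives about 17-30% power at OR 1.3 and 30-59% at OR 1.5, against 7-11% and 11-17% for a 2-3% flag. With two terms (2 df), the formula gives 13-24% and 25-52%.

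**The case against.** The strongest reply is that the 2-3% reading is not what the protocol says. The Introduction separates referred children from a larger poor-growth group, and it is the latter that motivates Aim 2; section 10.2 also plans several cut-offs. This stands. A reader might infer that Aim 2 rests on 12 to 18 flagged children and will probably fail, but the documents do not support that. A reader might also infer that only velocity could widen the flag, so that a flag near 10% is impossible at baseline. Section 9.5 applies parental height at baseline, so the baseline flag size is simply unknown. What survives is that a 10% flag still keeps only about a third of the information.

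Second, the coding of a covariate is usually left to the statistical analysis plan, which is not at hand, and the wider wording of the hypothesis and outcome leaves room for continuous terms. That is why this is a suggestion and not an error. It is still worth making because section 10.2 does name the model term, and names it more narrowly than the hypothesis it serves.

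Third, the flag fits the question whether growth failure is a useful marker. This stands too, and it counts against putting flag and continuous terms into one model. Under a purely graded effect the flag's odds ratio adjusted for SDS is centred near 1, although the unadjusted value is about 2.6-2.7 for a 2-3% flag. A useful marker could then look useless.

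**Conclusion.** The concern holds as a cheap improvement. The only growth term named for the delay models is, on its natural reading, a category, and a category between 2% and 10% keeps 12-34% of the information in a graded score. At n=600 and an odds ratio of 1.5 per SD, power is 24-47% (2-3% flag) or 46-76% (10% flag), against 82-99% for a single continuous score, or 76-99% with two continuous terms. The loss matters for mild to moderate gradients. A strong gradient (2.0) is usually found by either coding, and a step at the extreme is better found by the flag. The figures rest on assumed delay prevalence (10-30%), a normal score, a linear gradient and a 5% test, none of which the protocol states. They do not show that the planned model is wrong or that the flag should be dropped.

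**What to change.** In section 10.2, Aim 2, keep the flag model as planned, because it answers the marker question. Beside it, fit the same socioeconomic model with continuous height-for-age SDS and distance from target height in place of the flag, plus growth velocity where the follow-up ASQ-3 is the outcome. Take the growth measures from the same visit as the developmental outcome. For both models report the change in fit and the estimates with confidence intervals. Do not read a flag coefficient adjusted for SDS as the value of the marker. SDS and distance overlap, so judge the continuous model by its joint change in fit; section 10.2 already plans a co-linearity check for the algorithm's variables.

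The cost is one extra model and a second comparison to report and interpret. Child and parental heights are already collected, so no new data or visits are needed. The GMDS results should be described as imprecise under either model.
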